## **PRÉCIS**

### **Background:**

- Enzalutamide is currently approved for the treatment of patients with mCRPC
- The marketed (reference) formulation of enzalutamide is a liquid-filled, soft gelatin capsule containing 40 mg enzalutamide dissolved in Labrasol; four such capsules are required to deliver a 160 mg dose
- The four-capsule regimen is inconvenient because of the number of capsules that must be taken, particularly in light of the fact that cancer patients usually have to take multiple drugs.
- Additionally, some patients may not be able to swallow pills; therefore, alternate methods of oral administration are necessary

### **Objectives:**

- To evaluate the bioequivalence, safety, and tolerability of two oral formulations of enzalutamide following a single 160 mg dose in male subjects with prostate cancer under fasting conditions.

### **Eligibility:**

- Male subjects with prostate cancer

### **Design:**

- Comparative, randomized, open-label, single-dose, 2-way crossover bioavailability, safety and tolerability study
- Subjects will be randomized in Period 1 to one of two sequences: AB or BA. Following a minimum 42-day washout period, subjects will be crossed over in Period 2 to receive the treatment that they did not receive in Period 1.
- Treatment A will be the standard capsule (reference) formulation; Treatment B will be the liquid formulation (test product)
- Blood samples will be collected for pharmacokinetic analysis

*Abbreviated Title: Enzalutamide Formulation PK*  
*Version Date: 03.11.2020*

## **1 INTRODUCTION**

### **1.1 STUDY OBJECTIVES**

#### **1.1.1 Primary Objective**

- To evaluate the bioequivalence of two oral formulations of enzalutamide following a single 160 mg dose in male subjects with prostate cancer

#### **1.1.2 Secondary Objective**

- To evaluate the safety and tolerability of two oral formulations of enzalutamide following a single 160 mg dose in male subjects with prostate cancer.

### **1.2 BACKGROUND AND RATIONALE**

It is expected that 26,120 men will die from prostate cancer in the US in 2016 [1]. While some men are definitively treated for localized disease, many men will ultimately develop castrate resistant prostate cancer (CRPC) and succumb to the disease. Treatment options typically involve radical prostatectomy (RP) or radiation therapy in combination with androgen deprivation therapy. Following RP upwards of 50% of patients with high-risk disease will experience a biochemical recurrence at 5 years [2], and approximately 30% will die of their disease in 10-15 years [3].

#### **1.2.1 Enzalutamide Background**

Oral enzalutamide (160mg once daily) is currently approved in more than 40 countries for the treatment of metastatic castration-resistant prostate cancer (mCRPC). Enzalutamide acts on several steps of the androgen receptor (AR) pathway by inhibiting binding of androgen to the ligand binding domain of the AR, translocation of AR to the nucleus, and interaction of AR with DNA [4]. The efficacy and safety of enzalutamide was assessed in two randomized, placebo-controlled, multicenter phase III clinical trials (AFFIRM and PREVAIL) [5, 6].

Enzalutamide is a Biopharmaceutics Classification System (BCS) class 2 drug substance (low solubility, high permeability). It has been previously shown that lipid-based formulations work well with this drug class. The commercial product is a liquid-filled, soft gelatin capsule containing 40 mg enzalutamide dissolved in caprylocaproyl polyoxylglycerides (Labrasol).

#### **1.2.2 Pharmacokinetic Studies**

Multiple clinical pharmacokinetic studies of enzalutamide have been conducted [7]. Enzalutamide has a half-life of 5.8 days, achieves steady state by day 28, accumulates 8.3-fold with once-daily dosing, shows approximate dose proportionality from 30–360 mg/day, and has <30 % intersubject variability. It is primarily eliminated by hepatic metabolism, while renal excretion is an insignificant elimination pathway for enzalutamide and its active metabolite, N – desmethyl enzalutamide. Exposure to enzalutamide active moieties is not affected by food or baseline mild or moderate hepatic impairment. Enzalutamide has predictable pharmacokinetics, with low intersubject variability. Similar efficacy was observed in patients across the concentration/exposure range associated with a fixed oral dose of enzalutamide 160 mg/day.

*Abbreviated Title: Enzalutamide Formulation PK*  
*Version Date: 03.11.2020*

Study NCT01911715 was a phase I, open-label, one-period, single-dose mass balance and biotransformation study in six healthy male subjects [7]. After a single oral dose of enzalutamide 160 mg (4 x 40 mg capsules), at least 84.2% of the drug was absorbed. The average  $C_{max}$ ,  $t_{max}$ ,  $AUC_{inf}$ , and  $t_{1/2}$  of enzalutamide were 4.5 ug/mL, 1.8 h, 237 ug\*h/mL, and 2.9 days, respectively.

A phase I, open-label, randomized, single-dose, parallel design, food-effect study was performed in 60 healthy men (n=30 in fasted and fed arms) to determine the effect of a high-fat meal on the pharmacokinetics of enzalutamide [7]. The average  $C_{max}$  and  $T_{max}$  for the fasted and fed arms were 5.3 and 3.7 ug/mL and 1 and 2h post-dose, respectively. The average  $AUC_{inf}$  for the fasted and fed arms were 292 and 285 ug\*h/mL, respectively. In all, the data suggest that consumption of a high-fat meal slightly slows the rate of absorption but does not lower exposure of enzalutamide.

Gibbons et al. conducted two phase I drug interaction studies: one investigating the effects of coadministered drugs on the pharmacokinetics of enzalutamide, and one investigating the effects of enzalutamide on the pharmacokinetics of coadministered drugs [8]. Study NCT01913379, which used a parallel-treatment design (n=41), studied the effects of a strong CYP2C8 inhibitor (p.o. gemfibrozil 600 mg twice daily) and a strong CYP3A4 inhibitor (p.o. itraconazole 200 mg once daily) on the pharmacokinetics of enzalutamide after a single dose of enzalutamide (160 mg). Coadministration of gemfibrozil and itraconazole increased the  $AUC_{inf}$  of enzalutamide by 2.2- and 1.3-fold, respectively. Study NCT01911728, which used a single-sequence cross-over design (n=14), studied the effects of enzalutamide (160 mg/day) on the pharmacokinetics of a single oral dose of sensitive substrates for CYP2C8 (picoglitazone 30 mg), CYP2C9 (warfarin 10 mg), CYP2C19 (omeprazole 20 mg), or CYP3A4 (midazolam 2 mg). The  $AUC_{inf}$  of warfarin, omeprazole, and midazolam were decreased by 56, 70, and 86%, respectively, after coadministration of enzalutamide, suggesting that enzalutamide is a moderate inducer of CYP2C9 and CYP2C19 and a strong inducer of CYP3A4.

A randomized, two-period crossover pilot bioequivalence and food effect study was carried out in 60 healthy male subjects to compare two enzalutamide formulations [9]. The reference formulation, which had previously been used in human clinical trials, was a liquid-filled soft gelatin capsule containing 40 mg enzalutamide dissolved in Laprasol. Four capsules were necessary to deliver 160 mg enzalutamide. The test formulation was a tablet composed of 160 mg enzalutamide in a 60%A:hydroxypropyl methylcellulose acetate succinate (HPMCAS)-M spray dried dispersion. While cohorts A and B (n=15, each) were fasted, cohorts C and D (n=15, each) were fed. Cohorts A and C were given a single dose of 160 mg enzalutamide as a tablet. Cohorts B and D were given a single dose of 160 mg enzalutamide as 4x40 mg liquid-filled capsules. After a 42-day washout, cohorts A and B, C and D were crossed over. The average  $AUC_{day1-7}$  for the tablet and capsule formulations in fasted subjects was 177 and 185 ug\*h/mL, respectively. The average  $AUC_{day1-7}$  for the tablet and capsule formulations was 191 and 187 ug\*h/mL, respectively. In all, the data suggest that the bioequivalence of the formulations was comparable.

*Abbreviated Title: Enzalutamide Formulation PK*  
*Version Date: 03.11.2020*

### 1.2.3 Rationale for an Oral Formulation of Enzalutamide

The reference formulation is a liquid-filled, soft gelatin capsule containing 40 mg enzalutamide dissolved in Labrasol; four such capsules are required to deliver a 160 mg dose. The liquid-filled capsule formulation had previously been used in clinical studies in castration-resistant prostate cancer and is currently the marketed formulation. The four-capsule regimen is inconvenient because of the number of capsules that must be taken per dose, particularly in light of the fact that cancer patients often have to take multiple drugs. In addition, some patients may have difficulty with swallowing. Therefore, alternate methods of oral administration are necessary.

### 1.2.4 Summary

This is a single-dose randomized, open-label, 2-way crossover pilot bioequivalence study to compare two oral formulations of enzalutamide. The reference formulation is a liquid-filled, soft gelatin capsule containing 40 mg enzalutamide dissolved in Labrasol; four such capsules are required to deliver a 160 mg dose. The test formulation is a liquid enzalutamide formulation prepared by extracting the liquid from the gelatin capsule. Patients will be dosed under fasting conditions, which involve nothing to eat or drink 2 hours prior to dosing and 2 hours after dosing is complete. The pharmacokinetics of each method of administration will be studied to see if a liquid formulation of enzalutamide is a viable alternate to dosing as a capsule.

## 2 ELIGIBILITY ASSESSMENT AND ENROLLMENT

### 2.1 ELIGIBILITY CRITERIA

#### 2.1.1 Inclusion Criteria

2.1.1.1 Patients must have histologically or cytologically confirmed prostate cancer . Note: If histopathological documentation is unavailable, a clinical course consistent with prostate cancer is acceptable.

2.1.1.2 ECOG performance status 0 to 2 ( see [APPENDIX A](#))

2.1.1.3 Patients must have adequate organ and marrow function as defined below:

- |                             |  |
|-----------------------------|--|
| - Hemoglobin                | ≥ 9 g/dL   |
| - leukocytes                | ≥ 3,000/mcL  |
| - absolute neutrophil count | ≥ 1,500/mcL  |
| - platelets                 | ≥ 150,000/mcL  |
| - total bilirubin           | within normal institutional limits   |
| - AST(SGOT)/ALT(SGPT)       | ≤3 X institutional upper limit of normal   |
| - creatinine                | within normal institutional limits   |
|                             | OR   |
| - creatinine clearance      | ≥ 30 mL/min/1.73 m  for patients with creatinine levels above institutional normal (calculated via Cockcroft-Gault equation) |

2.1.1.4 Patients must not have other concurrent malignancies (within the past 2 years with the exception of non-melanoma skin cancer and Rai Stage 0 chronic lymphocytic leukemia), in situ carcinoma of any site, or life threatening illnesses, including untreated

*Abbreviated Title: Enzalutamide Formulation PK*  
*Version Date: 03.11.2020*

- infection (must be at least 1 week off intravenous antibiotic therapy before beginning enzalutamide).
- 2.1.1.5 Ability of subject to understand and the willingness to sign a written informed consent document.
  - 2.1.1.6 Willingness to travel to NIH for follow-up visits.
  - 2.1.1.7 Men age  $\geq$  18 years of age. Children are excluded because prostate cancer is not common in pediatric populations. Women are not eligible because this disease occurs only in men
  - 2.1.1.8 The effects of enzalutamide on the developing human fetus are unknown. For this reason men must agree to use adequate contraception (hormonal or barrier method of birth control; abstinence) throughout the course of the study and for 3 months after the last dose. Should a woman become pregnant or suspect she is pregnant while her partner is participating in this study, she should inform her treating physician immediately.
- 2.1.2 Exclusion Criteria
- 2.1.2.1 Patients who are receiving any other investigational agents (in the past 28 days) or herbal medications (within 7 days).
  - 2.1.2.2 Patients must not be on enzalutamide within five half-lives before the first planned dose of the study drug or anticipating to start enzalutamide within the next 3 months of the first planned dose of study drug
  - 2.1.2.3 History of allergic reactions attributed to compounds of similar chemical or biologic composition to enzalutamide or other agents used in study.
  - 2.1.2.4 Clinically significant cardiac disease, e.g. New York Heart Association (NYHA) classes III-IV; uncontrolled angina, uncontrolled arrhythmia or uncontrolled hypertension, myocardial infarction in the previous 6 months as confirmed by an electrocardiogram (ECG).
  - 2.1.2.5 Uncontrolled intercurrent illness including, but not limited to, ongoing or active infection, symptomatic congestive heart failure, unstable angina pectoris, cardiac arrhythmia, or psychiatric illness/social situations that would limit compliance with study requirements
  - 2.1.2.6 Patients who are taking medications that may alter the metabolism of enzalutamide. This includes the following: strong or moderate CYP2C8 inhibitors or inducers; strong CYP3A4 inhibitors or inducers; or CYP2C9, 2C19 or 3A4 substrates with a narrow therapeutic index. For a current table of Substrates, Inhibitors and Inducers please access the following website:  
<http://www.fda.gov/Drugs/DevelopmentApprovalProcess/DevelopmentResources/DrugInteractionsLabeling/ucm093664.htm>
  - 2.1.2.7 History of seizure, including any febrile seizure, loss of consciousness, or transient ischemic attack, or any condition that may pre-dispose to seizure (e.g. prior stroke,

*Abbreviated Title: Enzalutamide Formulation PK*  
*Version Date: 03.11.2020*

brain arteriovenous malformation, head trauma with loss of consciousness requiring hospitalization).

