### 2.1.3 Recruitment Strategies

This protocol may be abstracted into a plain language announcement posted on NIH websites and on NIH social media platforms. Participants will be recruited from the current patient population at NIH.

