## 3 STUDY IMPLEMENTATION

### 3.1 STUDY DESIGN

This is a randomized, open-label, single-dose, 2-way crossover, pilot bioavailability trial evaluating two oral formulations of enzalutamide. All men (n=12-14) enrolled in the trial will receive oral enzalutamide in two formulations: Treatment A will be the standard liquid-filled, soft gelatin capsule (reference) formulation; Treatment B will be the liquid formulation (test product). Subjects will be randomized in Period 1 to one of two sequences: AB or BA. Following a minimum 42-day washout period, subjects will be crossed over in Period 2 to receive the treatment that they did not receive in Period 1. Blood samples will be collected for pharmacokinetic analysis.

Subjects are admitted to the Clinical Center on Day 1 (for the first 24-hours of PK sampling) and will take a single 160mg dose of enzalutamide. They are to return to the Clinical Center on Day 3 for the 48h, on Day 8 for the 168h, and Day 42 for the post-dose blood draws. After an appropriate washout period (at least 42 days), subjects will be crossed over in Period 2 to receive the treatment that they did not receive in Period 1. Subjects will be re-admitted to the Clinical Center to receive the study drug and blood samples will be drawn as described above on Days 1, 3, 8, and 42. Drug Administration

*Abbreviated Title: Enzalutamide Formulation PK*  
*Version Date: 03.11.2020*

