## 5 BIOSPECIMEN COLLECTION

### 5.1 CORRELATIVE STUDIES FOR RESEARCH/PHARMACOKINETIC STUDIES

The time of enzalutamide dose administration is  $t = 0$  for purposes of pharmacokinetic sample collection times. Due to the long  $t_{1/2}$  of enzalutamide, *N*-desmethyl enzalutamide, and the carboxylic acid metabolite in healthy subjects (approximately 6, 8, and 10 days, respectively [7]), pharmacokinetic samples will be collected over 42 days.

With each 160 mg dose of enzalutamide, pharmacokinetic blood samples will be collected in 6-mL tubes with dipotassium ethylenediaminetetraacetic acid (K2 EDTA) as the anticoagulant. Venous blood samples for plasma will be collected at the following times: pre-dose (0 hr) and post-dose at 30 minutes; and at 1, 2, 4, and 8 hours (Day 1), 24h (Day 2), 48h (Day 3), 168h (Day 8), and Day 42 post-dose.

Validated bioanalytical methods based on ultra high-performance liquid chromatography with tandem mass spectrometry (uHPLC-MS/MS) [10] will be developed by the Clinical Pharmacology Program and used to analyze plasma samples for concentrations of enzalutamide and the two major human metabolites (e.g. *N*-desmethyl enzalutamide and carboxylic acid enzalutamide).

Non-compartmental PK analysis of enzalutamide in plasma will be performed using WinNonlin 5.0 (Pharsight, Inc., Mountain View, CA). PK parameters derived from plasma concentration-time data may include  $C_{max}$ ,  $T_{max}$ , AUC, Cl, Cl/F, Vd, and  $t_{1/2}$ .

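### Drug left over from earlier enzalutamide use stays in the Period 1 AUC: a former daily user exactly at the five-half-life limit brings in about 26% of one dose, and the visible plan has no rule to remove it

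*Combined protocol and SAP*

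**What the plan says.** - **Entry (2.1.2.2).** "Patients must not be on enzalutamide within five half-lives before the first planned dose of the study drug". Neither the half-life nor a number of days is given. Prior use is limited in time, not barred.
- **Recruitment (2.1.3).** "Participants will be recruited from the current patient population at NIH".
- **Kinetics (1.2.2).** "Enzalutamide has a half-life of 5.8 days, achieves steady state by day 28, accumulates 8.3-fold with once-daily dosing". The same section reports a six-subject mass-balance study with a mean half-life of 2.9 days ("and 2.9 days, respectively"). Section 5.1 justifies the sampling span by half-lives of the drug and its two metabolites "in healthy subjects (approximately 6, 8, and 10 days, respectively [7"]).
- **Washout (3.1).** "Following a minimum 42-day washout period, subjects will be crossed over in Period 2".
- **Sampling and PK (5.1).** With each dose, blood is drawn "pre-dose (0 hr) and post-dose at 30 minutes", then at intervals to Day 42. "Non-compartmental PK analysis of enzalutamide in plasma will be performed using WinNonlin 5.0".
- **Analysis (8.3, 8.4.2).** The population requires both administrations and blood on at least three of four dates in each. The AUC difference is then tested by a non-parametric crossover method.

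None of 5.1, 8.1, 8.3 or 8.4 says what happens when the pre-dose level is measurable. Section 5.2 was not in the text available for this review, so this statement covers only the visible PK and statistics sections, where such a rule would normally sit.

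**The concern.** Five half-lives sounds like near-complete elimination, and after a single dose it is: 1/32, or 3%, remains. A man who has taken the drug daily to steady state starts from about eight doses, so the same interval leaves about eight times as much. The plan's own between-period washout is far stricter, leaving under 1% of a single dose.

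The residue falls almost wholly in Period 1, and so on whichever formulation that patient takes first. In a 12-patient crossover with an equivalence band only 40 ug\*h/mL wide, one such patient can add noticeable noise to the formulation difference. Without a rule, the choice to correct, exclude or ignore him would be made with open-label data in hand.

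**Working it through.** **Inputs.** Half-life 5.8 days, accumulation 8.3, single-dose AUCinf 237 and 292 (fasted), Cmax 4.5 and 5.3 ug/mL (1.2.2). Six patients per sequence, SD of differences 20, true difference -20, limits -40 and 0, 5% per test (8.2). Washout 42 days (3.1).

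**Reproducing the plan's figures.**
- Mean accumulation on daily dosing = half-life/ln 2 = 5.8/0.693 = 8.37, in line with the stated 8.3.
- Two one-sided t-tests with the 8.2 inputs give 78.4% power at N = 10 and 88.4% at N = 12. Twelve is therefore the smallest balanced size reaching 80%.

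**Residue, as a share of one dose.**
- Start of Period 1, exactly at the limit: 8.3 × 2^-5 = 0.259.
- Start of Period 2: 0.259 × 2^(-42/5.8) = 0.0017.
- Ordinary carry-over of the Period 1 dose: 2^(-42/5.8) = 0.0066.
- With 2.9 days for both accumulation and window: (2.9/0.693)/32 = 0.131.

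**AUC added to Period 1** (terminal-phase decline; share × AUCinf × fraction inside the interval).
- 7 days, fraction 1 - 2^(-7/5.8) = 0.567: 0.259 × 237 × 0.567 = 35; with 292, 43.
- 42 days, fraction 0.993: 61 and 75.
- 2.9-day case, AUCinf 237: 0.131 × 237 = 31 over 42 days, and 25 over 7 days (fraction 0.812).

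**Shift in a mean-based estimate from one such patient** (residual AUC/12): about 3-4 ug\*h/mL (7-day) or 5-6 (42-day). The sign depends on his randomised sequence.

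**Effect on power.** Simulation with exact Wilcoxon two one-sided tests, 6 v 6, normal differences, one affected patient randomly allocated. Figures are good to about one percentage point.

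| Case | 7-day AUC | 42-day AUC |
|---|---|---|
| No residue | 84% | 84% |
| Exactly at the limit | 69-74% | 51-58% |
| Spread over the first half-life past it | 76-78% | 61-68% |
| At the limit, 2.9-day case | 78% | 76% |
| Subtracted, 20% error | 83-84% | 82-83% |
| Subtracted, 40% error | 81-82% | 77-79% |
| Subtracted, 53% error | 80-81% | 74-77% |
| Excluded, not replaced (6 v 5) | 76% | 76% |

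The mean estimate stays at -20. Its SD rises from 6.0 to 6.6-6.8 (7-day) or 7.0-7.1 (42-day). At a true difference of -40 or 0 the rejection rate is 4.5-4.7%, with or without the residue.

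The 42-day column uses the 8.2 limits as written, although those imply an AUC near 200 (10% is about 20). If limits and SD are scaled up to a 42-day AUC from a base of 185-200, the added amount is 61/(237/200) = 51 to 61/(237/185) = 48 in 8.2 units, and power at the limit is 63-66%.

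**Pre-dose level.** k = ln 2/(5.8 × 24 h) = 0.00498 per hour.
- C0 at the limit = 0.259 × AUCinf × k = 0.306 or 0.377 ug/mL. As a share of observed Cmax: 0.306/(4.5 + 0.306) = 6.4%; 0.377/(5.3 + 0.377) = 6.6%.
- At six half-lives: 3.3-3.4%.
- Ordinary Period 2 pre-dose level: 237 × k × 0.0066 = 0.0078, or 0.0096 with 292; about 0.2% of Cmax.

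**The case against.** **The case may never arise.** This stands. The documents give no count of former users. If, purely as an assumption, 1 to 6 of 12 were former daily users with stop dates spread evenly over the previous 180 to 730 days, the chance of at least one within a half-life of the limit would be 1-21%. The loss also halves quickly with time off drug. The argument for acting is that the remedy is cheap, not that the case is likely.

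**A reader might infer bias toward one formulation, or a raised false-positive rate.** Neither follows. Sequence is randomised, the residue adds to Period 1 under either order, and the simulated type I error stays below 5%.

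**A reader might infer that the limit could be counted with 2.9 days while the true half-life is 5.8, leaving 8.3 × 2^(-14.5/5.8) = 1.5 doses.** The documents do not say this. Their 5.8 and roughly 6 days give almost the same limit (29-30 days), and 2.9 days comes from one six-subject study. The unnamed half-life is a loose end to tidy, not evidence of a short window.

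**Subtraction is not always better than exclusion.** This also stands. If Day 42 is not quantifiable, error in k could make the 42-day subtraction wrong by 35-53%. At 53%, power is 74-77%, no better than the 76% from exclusion. Section 8.3 also lets a patient miss one of the four dates, so Day 42 may be absent. And 8.2 allows up to 14 patients to reach 12 evaluable, so an excluded patient might be replaced and the power recovered.

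**The AUC interval is not stated, and 8.4.2 describes a difference test, not an equivalence test.** Both are correct. The power figures therefore rest on a stand-in for the 8.2 test. The study calendar also marks PK at screening and baseline, but 5.1 does not describe those samples, so they cannot be counted on.

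**Conclusion.** The point holds as a minor, conditional one. On the documents' own figures, the entry rule can let in about 26% of a dose (13% on the 2.9-day figure), nearly all of it in Period 1, and the visible analysis leaves it in the AUC although the sample that would reveal it is taken. The consequence is lost precision and chance imbalance only. The power losses apply to one former steady-state daily user at or just past the limit and should not be read as the trial's expected power.

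The figures assume linear kinetics, terminal-phase decline, a prior daily dose equal to the study dose, AUCinf of 237 and 292 paired with a 5.8-day half-life (the 237 comes from the study that reported 2.9 days), and rank-based two one-sided tests. A reader might also doubt the 42-day washout between periods; at 0.66% of a dose remaining, these figures give no ground for that.

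**What to change.** 1. **State the primary AUC interval T.** The rule below needs it.
2. **Add a rule to 5.1, applied before 8.4.2.** Where the pre-dose level C0 is quantifiable, subtract C0 × (1 - exp(-kT))/k from that period's AUC. Estimate k from the patient's own terminal samples (48 h, 168 h, Day 42), pooled over both periods.
3. **State when the subtracted AUC is primary:** when k is adequately estimated, meaning Day 42 is quantifiable or T is 7 days. Power is then about 82-84% at 20% error.
4. **Pre-specify a sensitivity analysis** excluding patients whose pre-dose level exceeds a set share of that period's observed Cmax, and rely on it when k is poorly estimated. The cut-off should lie between about 0.2% (ordinary carry-over) and 6.4% (patient at the limit). A value of 3%, for example, would catch both the five- and six-half-life cases. Say whether an excluded patient counts as non-evaluable under the ceiling of 14.
5. **Reconcile 2.1.2.2** with the half-lives in 1.2.2 and 5.1 and with the stated accumulation. No window length is proposed here.

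**Cost.** The subtraction needs no new samples and has no accrual cost. The downside is a little extra analysis and some error in k. With an assumed 15% assay CV, the subtraction error is about 15-16% with all three terminal samples. Without a quantifiable Day 42 (about 8-10 ng/mL expected; the visible text gives no assay limit), it is 18-20% for a 7-day AUC and 35-53% for a 42-day AUC.

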### 3.3 STUDY CALENDAR

Procedure	Screening	Baseline	Period 1					Period 2				
			Day 1	Day 2	Day 3	Day 8	Day 42	Day 1	Day 2	Day 3	Day 8	Day 42
Confirmation of diagnosis	X	X										
History and PE	X	X	X g				X	X d				X
Vital signs	X	X	X			X	X	X d				X
Performance Score	X	X					X	X d				X
Labs	X a	X b	X f				X	X d				X
Urinalysis	X	X					X	X d				X
ECG	X	X					X	X d				X
PK c	X	X	X	X	X	X	X	X	X	X	X	X
Adverse Events			X	X	X	X	X	X	X	X	X	X
Concomitant Medications			X			X	X	X d			X	X
Questionnaire			X e					X e				

aFor screening labs see Section 2.2

bFor baseline labs see Section 2.4;

cSee Section 5.1 for complete details.

dWith the exception of PK and adverse events, all assessments and labs on Period 2 Day 1 do not need to be repeated if within 8 days of Period 1 Day 42.

eSubjects will be given a questionnaire (see APPENDIX B) to complete following the administration of the liquid (test) formulation to assess the tolerability. The questionnaire is only completed on the day the liquid formulation is administered. It is not necessary to complete the questionnaire on the day the capsule formulation is administered.

fLabs do not need to be repeated if they were completed at screening/baseline within 17 days of of period 1 day 1.

gH&P may be performed within 17 days of treatment initiation.

*Abbreviated Title: Enzalutamide Formulation PK*  
*Version Date: 03.11.2020*

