### 4.1 GENERAL GUIDELINES

All medications (other than study drug) and significant non-drug therapies (including physical therapy and blood transfusions) taken within 28 days of starting study treatment through the follow up visit should be reported on the CRF.

While patients are on protocol treatment, all medications required for the health of the patient are allowed with the following exception: concomitant use of herbal supplements.

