## **8 STATISTICAL CONSIDERATIONS**

### **8.1 STATISTICAL HYPOTHESES**

#### **Primary efficacy endpoints:**

To evaluate the bioequivalence of two oral formulations of enzalutamide following a single 160 mg dose in male subjects with prostate cancer.

The primary measure of efficacy will be AUC for the first period of administration obtained during blood draws during visits on day 1, 3, 8, and 42 evaluations, and then AUC at a second set of visits at least 42 days after the first administration, for evaluations on days 1, 3, 8 and 42 relative to the second administration, for the second period evaluations.

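### The entry exclusion for planned enzalutamide runs 3 months from the first dose, but the last primary-endpoint sample is timed from the second dose and the washout has no maximum, so the window can close before that sample is drawn

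*Combined protocol and SAP*

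**What the plan says.** - **Entry screen (2.1.2.2).** The forward-looking half excludes men "anticipating to start enzalutamide within the next 3 months of the first planned dose of study drug". The clock starts at dose 1.
- **Washout (3.1).** "After an appropriate washout period (at least 42 days), subjects will be crossed over in Period 2". The Précis, 2.3.1, 3.2 and 8.1 also give 42 days only as a minimum. No section gives a maximum.
- **Primary endpoint (8.1).** The Period 2 measure is "AUC at a second set of visits at least 42 days after the first administration". Its sampling days are counted from dose 2 and include Day 42, so that sample is part of the primary AUC.
- **Sampling (5.1).** The late samples are "24h (Day 2), 48h (Day 3), 168h (Day 8), and Day 42 post-dose". Nothing is drawn between 168 h and Day 42.
- **Calendar (3.3, footnote d).** The footnote, which leaves out PK sampling and adverse-event recording, says that "all assessments and labs on Period 2 Day 1 do not need to be repeated if within 8 days of Period 1 Day 42". A gap of up to 8 days between the periods is thus foreseen, and a longer one only triggers repeat assessments.
- **Concomitant medication (4.1).** During study treatment the rule is that "all medications required for the health of the patient are allowed with the following exception: concomitant use of herbal supplements". Non-study enzalutamide is not named.
- **Analysis population (8.3).** A man is kept if he took both administrations and had blood drawn on at least three of the four required dates after each. There is no condition about non-study enzalutamide.

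**The concern.** The exclusion evidently serves to keep a participant's own enzalutamide treatment out of the sampling period. A fixed window counted from dose 1 cannot guarantee that when the last sample moves with dose 2 and dose 2 has no latest date. All participants have prostate cancer, and section 1.2.1 describes enzalutamide as approved for metastatic castration-resistant disease, so a planned start is a realistic event.

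With no sample between 168 h and Day 42, the Day 42 concentration sets the end of a five-week AUC segment. Non-study drug present at that draw would be counted as exposure from the Period 2 formulation. The error falls only in Period 2, so it does not cancel within the man. It inflates the liquid in sequence AB and the capsule in sequence BA.

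**Working it through.** The documents state no total duration, so there is no plan figure to reproduce.

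**Calendar**

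Inputs: dose-to-dose gap G ≥ 42 days (3.1, 8.1). The Day 42 sample falls E = 41 days after its dose if the dosing day is Day 1, or E = 42 if read as 42 days post-dose (5.1). Three calendar months are W = 89–92 days, depending on the start date.

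The last sample falls T = G + E days after dose 1, and the slack is W − T.

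| Schedule | G | T | Slack |
|---|---|---|---|
| Shortest | 42 | 83–84 | 89 − 84 = 5 to 92 − 83 = 9 |
| Period 2 Day 1 is 8 days after Period 1 Day 42 | 49–50 | 90–92 | 89 − 92 = −3 to 92 − 90 = +2 |
| Illustration | 56 | 97–98 | 89 − 98 = −9 to 92 − 97 = −5 |
| Illustration | 70 | 111–112 | 89 − 112 = −23 to 92 − 111 = −19 |

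In the second row the same reading of Day 42 is used in both periods (49 + 41 = 90, 50 + 42 = 92). Break-even is G = W − E, from 89 − 42 = 47 to 92 − 41 = 51 days.

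**Size of the effect on one man's AUC (assumption-based)**

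Assume one non-study 160 mg dose 24 h before the Day 42 draw, mono-exponential decline, and a linear trapezoid from 168 h to 1008 h (840 h, so an added concentration is multiplied by 420 h). Section 5.1 names no integration rule. Section 1.2.2 gives a half-life of 5.8 days, so k = ln 2 / (5.8 × 24) = 0.00498 per h. It also gives AUCinf of 237 (mass-balance study) and 292 (food-effect study, fasted), and an AUC day 1–7 of 185 (fasted capsule, pilot tablet study), all in ug*h/mL.

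1. *From the tail area.* C168 = (AUCinf − 185) × k = 52k to 107k = 0.26–0.53 ug/mL. C24 = C168 × exp(144k) = 0.53–1.09 ug/mL. Added area = 0.53 × 420 to 1.09 × 420 = about 220–460 ug*h/mL.
2. *From AUCinf alone.* C24 = AUCinf × k × exp(−24k) = 1.05–1.29 ug/mL. Added area = about 440–540 ug*h/mL.

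The uncontaminated Day 42 level under either approach is about 0.004–0.010 ug/mL.

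Sensitivity: with the 2.9-day half-life reported by the mass-balance study and its AUCinf of 237, the second approach gives C24 = 1.86 ug/mL and about 780 ug*h/mL by the linear rule, or about 920 with linear-up, log-down.

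One such man among 12 would move a mean Period 2 AUC, or a mean period difference, by 220/12 to 540/12 = about 18–45 ug*h/mL. For scale, the lower equivalence limit in 8.2 is −40 ug*h/mL.

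**Does another section close the gap?**

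- Section 4.3 restricts drugs given together with enzalutamide. Although 1.2.2 calls enzalutamide a strong CYP3A4 inducer, 4.3 does not list it or address non-study use.
- Section 3.5 names no such event; only general investigator discretion applies.
- Section 8.3 counts dates with blood drawn, and this man has them.

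**The case against.** The strongest reply is that the plan works at its shortest schedule: the window outlasts the last sample by about 5–9 days. Harm needs two further events, a Period 2 that starts about a week or more late and a man who starts enzalutamide before his final draw. The documents do not allow the frequency to be estimated. That stands.

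Other points also stand in part:

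- **Entry screen, not a ban.** A reader might infer that 2.1.2.2 forbids starting enzalutamide on study. It asks only what is anticipated at enrolment. Rewording it cannot prevent an unplanned start, which is why a data-handling rule is needed as well.
- **The 8-day case is borderline.** A reader might infer that the calendar's 8-day allowance always puts the last sample outside the window. It does not: the margin runs from −3 to +2 days.
- **The magnitude is fragile.** It combines figures from different studies, pairs a 5.8-day half-life with an AUCinf whose own study reports 2.9 days, and assumes an integration rule.
- **Effect on the test.** Sections 8.4.1 and 8.4.2 plan a non-parametric crossover analysis, so one extreme AUC has bounded leverage. The −40 limit appears only in the mean-based power statement. A mean shift of 18–45 should not be read as deciding the planned test.
- **It would not be hidden.** Concomitant medications are recorded on Period 2 Days 8 and 42 (3.3) and reported on the CRF (4.1), the team meets at least weekly during active treatment (7.5.1), and the Day 42 level would be far above expectation. These are ways to notice it. None says what to do with the sample.

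**Conclusion.** The mismatch is real and follows from the text alone: the exclusion is anchored to dose 1, the last primary-endpoint sample to dose 2, and nothing bounds the distance between them. Once the dose-to-dose gap passes about 47–51 days, depending on how days and months are counted, a man expected to start enzalutamide just after month 3 can be eligible, start before his last draw, and stay in the 8.3 population.

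The consequence for one man rests on assumptions: about 220–540 ug*h/mL added to his Period 2 AUC for a single dose 24 h before the draw, with the linear trapezoid and a 5.8-day half-life. The rank-based test limits what he does to the trial's inference, but his AUC, his rank and any reported mean would be wrong.

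The documents do not support saying that the shortest schedule is exposed, that contamination is likely, or that one such man would overturn the result. This is a worthwhile, inexpensive correction, not a fatal flaw.

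**What to change.** 1. **2.1.2.2.** Reword the forward-looking part to exclude men who expect to begin enzalutamide before the Period 2 Day 42 PK sample, in place of the three-month window.
2. **3.1.** Reconcile that wording with the open-ended washout, so that the end of the exclusion can be understood at enrolment. No interval value is proposed here.
3. **8.3.** State that samples drawn after any non-study enzalutamide are not used in the AUC and do not count toward the three-of-four-dates rule. A man who loses only Day 42 is then treated as 8.3 already treats a missing Day 42, and his AUC is taken over the same interval in both periods.

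None of this alters when a man receives treatment he needs; it changes eligibility and data handling only. The cost is a few sentences, with no added visit or sample. The downside is that an occasional man expected to start enzalutamide soon after month 3 is not enrolled. The 8.3 rule could also make a man unevaluable if he loses more than one date, and 8.2 allows only two men beyond the 12 evaluable (ceiling of 14).
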